5.7.5 Adverse Event Reporting

The Investigator will review each event and assess its relationship to drug treatment (unrelated, unlikely, possibly, probably, likely). Each sign or symptom reported will be graded on the NIH NCI CTCAE toxicity grading scale 5-point severity scale (Grade 1, 2, 3, 4 and 5). The date and time of onset, time relationship to drug dosing, duration, and outcome (resolved, improved, unchanged, worse, fatal, or unknown/lost to follow-up) of each event will be noted.

Unrelated	• The AE must clearly be caused by the subject's clinical state, or the study procedure/conditions.
	Definitely not related to drug.
	• Temporal sequence of an AE onset relative to administration of drug not reasonable.
	• Another obvious cause of an AE.
Unlikely	• Time sequence is unreasonable.
	• There is another more likely cause for an AE.
Possibly	Corresponds to what is known about the drug.
	• Time sequence is reasonable.
	• Could have been due to another equally, likely cause.
Probably	• Is a known effect of the drug.
	• Time sequence from taking drug is reasonable.
	Ceases on stopping the drug.
	• Cannot be reasonably explained by the known characteristics of the subject's clinical state.
Likely	• Is a known effect of the drug (e.g., listed in Physicians' Desk Reference, Compendium of Pharmaceuticals and Specialties, IB).
	• Time sequence from taking drug is reasonable.
	• Event stops upon stopping drug, event returns upon restarting drug.

The following CTCAE toxicity grading scale 5-point severity scale definitions for rating maximum severity will be used:

Grade 1	Mild; asymptomatic or mild symptoms; clinical or diagnostic observations only; intervention not indicated.
Grade 2	Moderate; minimal, local or noninvasive intervention indicated; limiting age- appropriate instrumental activities of daily living.*
Grade 3	Severe or medically significant but not immediately life-threatening; Hospitalization or prolongation of hospitalization indicated; disabling; limiting self-care activities of daily living.** Note: An experience may be severe but may not be serious, e.g., severe headache).
Grade 4	Life-threatening consequences; urgent intervention indicated.
Grade 5	Death related to AE.

Note: A semi-colon indicates 'or' within the description of the grade.

*Instrumental activities of daily living refer to preparing meals, shopping for groceries or clothes, using the telephone, managing money, etc.

**Self-care activities of daily living refer to bathing, dressing and undressing, feeding self, using the toilet, taking medications, and not bedridden.

AEs will be coded using the most current MedDRA[®] version available at the start of the study (e.g., 21.0 or higher).

5.8 Reporting Pregnancy

During study participation, all subjects should be instructed to contact the Investigator immediately if they suspect they might be pregnant (e.g., missed or late menstrual period). If pregnancy is confirmed, Investigational Product must be discontinued immediately, the subject should be referred to an obstetrician experienced in reproductive toxicity for evaluation and counseling, and the subject should be followed until the conclusion of the pregnancy.

The Investigator is responsible for reporting all available pregnancy information on the pregnancy report and submitting to the Medical Monitor within 24 hours of becoming aware of the event, although pregnancy itself is not considered an AE. Follow-up information detailing the outcome of the pregnancy and the health of the newborn should be reported as it becomes available. Any pregnancy complication must be reported as a SAE. In addition, any pregnancy resulting in a congenital abnormality or birth defect of the newborn, or neonatal death occurring within 30 days of the birth must be reported as a SAE, regardless of causality. Any infant death that occurs after the 30 day reporting period that the Investigator suspects is related to the Investigational Product must also be reported as a SAE.

Partner pregnancies of a male subject do not need to be reported.

5.9 Treatment Stopping Rules

If a subject has non-cutaneous adverse events of concern, clinically significant laboratory values or any condition that the Investigator determines could possibly be related to the IP, the Investigator should immediately contact the Medical Monitor to discuss if the subject should be discontinued from the investigational product.

Treatment for any individual subject will be discontinued if the subject:

- Experiences a serious adverse event (SAE) or a clinically significant non-serious AE which in the opinion of the Principal Investigator or Medical Monitor warrants discontinuation from the IP for that subject's well-being.
- A severe (Grade 3) laboratory abnormality (confirmed by repeat sample and considered related to IP).
 - See Appendix 6 for details.

Dosing of IP for an individual subject may be suspended for safety concerns other than those described above, at the discretion of the Investigator if he/she feels the subject's safety may be threatened.

A subject with a PHQ-8 score of '15' or above should be referred promptly to a mental health care professional and consideration be given to discontinuation from IP.

A subject that is experiencing suicidal ideation and behavior should be referred immediately to a qualified mental health care provider and consideration given to discontinuation from IP.

As noted above, study treatment must be discontinued immediately in the event of a female subject's pregnancy.

Treatment should be interrupted:

• If a subject develops an application site reaction with the clinical appearance of an 'irritation reaction', and with a severity of a Dermal Response Score of 5 (erythema, edema and papules) or greater on the scale of Berger and Bowman, treatment should be interrupted for up to one week and may then be resumed if the reaction has, in the opinion of the Investigator, adequately resolved.

Treatment should be discontinued:

• If the reaction reoccurs, treatment should be discontinued permanently, and the subject followed until the reaction resolves. Given the excellent local toleration in the Phase 1/2a study, such reactions are possible, but unlikely.

5.9.1 Emergency Unblinding

Treatment assignment should remain blinded unless the knowledge is necessary to determine emergency medical care, as determined by the Investigator. Emergency unblinding will be done using the study IWRS system in consultation with the Medical Monitor and the Sponsor's CMO. Blinding of study treatment is critical to the integrity of this clinical trial and therefore, if a subject's treatment assignment is disclosed to the Investigator, the subject will have the IP discontinued.

6 DATA ANALYSIS

Data will be handled and processed according to the Contract Research Organization's Standard Operating Procedures, which are written based on the principles of GCP.

6.1 Statistical Methods

The methodology presented below is a summary of the more detailed analysis plan that will be presented in the Statistical Analysis Plan (SAP). The SAP will be finalized before the database is locked and unblinded. Any changes to the methods described in the final SAP will be described and justified in the clinical study report.

All statistical processing will be performed using SAS[®] (Version 9.4 or later) unless otherwise stated.

Descriptive statistics will be used to provide an overview of the efficacy, safety and pharmacokinetic results. For categorical parameters, the number and percentage of subjects in each category will be presented. The denominator for percentage will be based on the number of subjects appropriate for the purpose of analysis. For continuous parameters, descriptive statistics will include n (number of subjects), mean, standard deviation (SD), median, minimum, and maximum.

P-values of less than 0.10 will be considered statistically significant based on a two-sided test unless otherwise specified. No adjustments for multiplicity are planned.

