6.3 Efficacy Evaluation

6.3.1 Primary Efficacy Endpoint

The primary efficacy variable in this study is success in Investigator Global Assessment (IGA) of disease severity, defined as an IGA score of 'Clear' or 'Almost Clear' plus a 2-grade improvement from Baseline at Week 8.

The primary endpoint will be analyzed using a Cochran-Mantel-Haenszel test stratified by the stratification factors study site and baseline disease severity. Statistical significance will be concluded at the 5% significance level (2-sided).

Missing IGA scores will be imputed using multiple imputation.

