6.3.2 Secondary Endpoints

The Secondary Efficacy Endpoints will include:

- Achievement of an IGA score of 'clear' or 'almost clear' PLUS a 2-grade improvement from Baseline at weeks 2 and 4
- Change from Baseline in Overall Assessment of Erythema score at weeks 2, 4, and 8
- Change from Baseline in Overall Assessment of Scaling score at weeks 2, 4, and 8
- Achievement of an Overall Assessment of Erythema (0-3 scale) score of 0 or 1 PLUS a 2-grade improvement from Baseline at weeks 2, 4, and 8
- Achievement of an Overall Assessment of Scaling (0-3 scale) score of 0 or 1 PLUS a 2grade improvement from Baseline at weeks 2, 4, and 8
- Change in WI-NRS pruritus score at weeks 2, 4, and 8, as compared to Baseline
- In subjects with a Baseline WI-NRS pruritus score of ≥4, achievement of a ≥4-point improvement from Baseline in WI-NRS pruritus score at weeks 2, 4, and 8

The binary endpoints will be analyzed using a Cochran-Mantel-Haenszel test stratified by study site and baseline disease severity similar to the primary endpoint.

The continuous endpoints will be analyzed using an analysis of covariance with treatment, study site, baseline disease severity, and baseline value as independent variables. Statistical comparison between the active treatment arm and vehicle arm will be facilitated by using contrasts.

The endpoints measuring change from baseline in overall assessment of erythema and scaling will be statistically tested using CMH row-mean scores test.

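### Secondary results are called statistically significant at p<0.10 with no multiplicity control and no gate on the primary, a looser bar than the 5% set for the primary endpoint

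*Protocol*

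**What the plan says.** Protocol section 6.1 sets a default for the whole study: "P-values of less than 0.10 will be considered statistically significant based on a two-sided test unless otherwise specified. No adjustments for multiplicity are planned".

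Only one place sets a different level for a test. Section 6.3.1 says of the primary endpoint: "Statistical significance will be concluded at the 5% significance level (2-sided".

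Section 6.3.2 lists seven secondary endpoints, nearly all at three visits, for example "Change from Baseline in Overall Assessment of Erythema score at weeks 2, 4, and 8" and "Change from Baseline in Overall Assessment of Scaling score at weeks 2, 4, and 8". It assigns a test to every one: stratified Cochran-Mantel-Haenszel (CMH) for binary endpoints, analysis of covariance for continuous ones, and a CMH row-mean scores test for change in erythema and scaling. It states no separate alpha, no testing order and no condition that the primary must succeed first.

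Section 6.3.3 lists exploratory endpoints without tests. Sections 6.5.2 and 6.5.3 name an analysis of covariance for DLQI and Scalpdex.

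**The concern.** Because 6.3.2 specifies no level of its own, the 0.10 default governs all secondary tests. The result is an inverted hierarchy. A Week 8 primary p-value of 0.07 would not be significant under 6.3.1, while a Week 2 scaling p-value of 0.09 would be statistically significant under 6.1. Nothing in the protocol prevents the second statement from being made after the first.

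What is at stake is what the clinical study report may conclude. The label normally tells a reader that the false-positive risk behind a claim was controlled at the stated level. For one of 20 unadjusted, ungated tests at 0.10 it was not. The primary test itself is unaffected.

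**Working it through.** **Plan's own figure.** The protocol gives no expected number of false positives and no family-wise error rate for the secondary endpoints, so there is nothing to reproduce.

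**Inputs.** The threshold is 0.10 two-sided, with no adjustment (6.1). The number of secondary tests comes from 6.3.2:

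| Secondary endpoint | Visits (weeks) | Tests |
|---|---|---|
| IGA success | 2, 4 | 2 |
| Change in erythema | 2, 4, 8 | 3 |
| Change in scaling | 2, 4, 8 | 3 |
| Erythema response | 2, 4, 8 | 3 |
| Scaling response | 2, 4, 8 | 3 |
| Change in WI-NRS | 2, 4, 8 | 3 |
| WI-NRS 4-point response | 2, 4, 8 | 3 |
| Total | | 20 |

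Each endpoint-visit pair is counted once. The per-protocol repeats in 6.1.2 are left out because they are labelled a sensitivity analysis.

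**Expected count under no effect.** k × α = 20 × 0.10 = 2.0. An expectation does not depend on correlation, so this holds however the endpoints are related. The tests are two-sided, so half of these favour the drug: 20 × 0.05 = 1.0.

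**Chance of at least one, if independent.**
- Either direction: 1 − 0.90^20 = 0.878.
- Favouring the drug: 1 − 0.95^20 = 0.642.

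**Chance of at least one, with correlation.** The protocol gives no correlations, so a common value ρ is assumed. Each test statistic is modelled as Z = √ρ·C + √(1−ρ)·E, with a shared standard normal C and independent standard normal E. A result favours the drug when Z > 1.645. Simulation with 200,000 draws and numerical integration over C agree:

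| Assumed ρ | At least one, either direction | At least one favouring the drug |
|---|---|---|
| 0 | 88% | 64% |
| 0.3 | 80% | 45% (0.445) |
| 0.5 | 66% | 34% |
| 0.7 | 48% | 24% |
| 0.9 | 27% | 14% |

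**Exploratory endpoints.** Those with a named test and not already counted are DLQI and Scalpdex at three visits each, which is six tests. They add 6 × 0.10 = 0.6, giving 2.6 expected in either direction and 1.3 favouring the drug. Section 6.3.3 lists 20 to 22 distinct comparisons once the repeated WI-NRS response item is removed; the range arises because the 2-grade IGA item names no visit. If all were tested, the expected total would be 4.0 to 4.2.

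**Alternative reading.** Section 6.3.2 says the binary endpoints are analysed in a way similar to the primary. If that carried the 5% level over to the 11 binary tests (2 + 3 + 3 + 3), the expected count would be 11 × 0.05 + 9 × 0.10 = 1.45. The sentence describes the test method, so 0.10 is the natural reading.

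**The case against.** The strongest reply is that this is an openly disclosed choice. Section 3.1 calls the trial a Phase 2a proof-of-concept study, section 6.1 says plainly that no adjustment is planned, and the protocol makes no confirmatory claim on any secondary endpoint. Section 6.1 also describes itself as a summary of a more detailed SAP, which could set how secondary p-values are presented. On this view, only a preference about wording remains.

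Much of that stands. No adjustment is required at this stage, and none is asked for here. But the protocol does not leave the label open for the SAP. It fixes both the threshold and the wording, and that wording determines what the report may claim.

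Four stronger readings are tempting and are not supported:

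- **Two false claims for the drug.** The 2.0 counts both directions. About 1.0 would favour the drug, and results favouring vehicle do not support a claim for it.
- **An 88% chance of a false claim.** This figure also counts both directions, and it assumes independence. The 20 tests use the same subjects, repeat the same scales across visits and pair change with response on each scale. The IGA grades are themselves defined by erythema and scaling (5.2.1). Substantial positive correlation is to be expected, which makes 88% an upper bound.
- **A doubling to about four from the exploratory endpoints.** This holds only if every listed exploratory endpoint is tested. The protocol names a test for six non-duplicate comparisons.
- **Programme expansion resting on these p-values.** The Synopsis and 6.1.3 tie expansion to the interim futility analysis, which has its own rule. Nothing links it to secondary p-values.

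**Conclusion.** The point holds as a matter of labelling. Sections 6.1, 6.3.1 and 6.3.2 together let 20 uncontrolled secondary tests be declared statistically significant at p<0.10, ungated, while the primary is held to 5%. Under no effect, 2.0 of the 20 are expected to reach that threshold, about 1.0 favouring the drug. The chance of at least one favouring the drug is 64% under independence and 24% to 45% for common correlations of 0.7 down to 0.3. Those correlations are assumptions; the expected counts do not depend on them.

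The looser-bar part of the point depends on 5% being the level for the primary. The Synopsis and 6.1.1 calculate power at a two-sided 0.10. If the sponsor settles on 0.10, the bars become equal, but the missing gate and the uncontrolled label remain.

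This is a worthwhile, inexpensive improvement. It does not undermine the primary analysis, and it does not show that the study needs a formal multiplicity procedure.

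**What to change.** First settle one alpha for the primary endpoint, so that 6.3.1 agrees with the Synopsis and 6.1.1. The label cannot be tied to the primary's level while the protocol carries two. The power statements then need to be checked against the chosen value.

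Then replace the default rule in 6.1 with a sentence saying that statistical significance will be concluded only for the primary endpoint at that level. It should add that p-values for secondary and exploratory endpoints are nominal, are reported with effect estimates and confidence intervals, and are not described as statistically significant.

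No endpoint, test, visit or subject changes. The cost is one sentence in 6.1 plus the alpha reconciliation. The downside is that the report can describe secondary results only as nominal, however small their p-values.

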6.1.1 Determination of Sample Size

A sample size of approximately 184 subjects are planned for the study.

The randomization scheme will be 2:1 (ARQ-154 foam 0.3% QD: matching vehicle QD). Randomization will be stratified by site and baseline disease severity (IGA = 3 or IGA = 4). Approximately 121 subjects will receive ARQ-154 foam 0.3% QD; approximately 63 subjects will receive vehicle foam QD.

A sample size of 184 subjects will provide approximately 90% power to detect an active response of at least 58.5%, assuming 159 subjects complete the study and a vehicle response of 30%, based on two-group X^2 test of equal proportions (without continuity correction), using a 2-sided alpha of 0.10.

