Study Endpoints	 The Primary Efficacy Endpoint will be defined as: Achievement of an IGA score of 'clear' or 'almost clear' PLUS a 2-grade improvement from Baseline at week 8

	The Secondary Efficacy Endpoints will include:
	• Achievement of an IGA score of 'clear' or 'almost clear' PLUS a 2-grade improvement from Baseline
	at weeks 2 and 4
	 Change from Baseline in Overall Assessment of
	Erythema score at weeks 2, 4, and 8
	• Change from Baseline in Overall Assessment of
	Scaling score at weeks 2, 4, and 8
	• Achievement of an Overall Assessment of Erythema
	(0-3 scale) score of 0 or 1 PLUS a 2-grade
	improvement from Baseline at weeks 2, 4, and 8
	• Achievement of an Overall Assessment of Scaling
	(0-3 scale) score of 0 or 1 PLUS a 2-grade
	improvement from Baseline at weeks 2, 4, and 8
	• Change in WI-NRS pruritus score at weeks 2, 4, and
	8, as compared to Baseline
	• In subjects with a Baseline WI-NRS pruritus score
	of \geq 4, achievement of a \geq 4-point improvement from
	Baseline in WI-NRS pruritus score at weeks 2, 4,
	and 8. Exploratory Endpoints will include:
,	 Change in Scalpdex total score from Baseline at
	weeks 2, 4, and 8
	 Achievement of an Overall Assessment of Erythema
	(0-3 scale) score of 0 or 1 at weeks 2, 4, and 8
	 Achievement of an Overall Assessment of Scaling
	(0-3 scale) score of 0 or 1 at weeks 2, 4, and 8
	• Achievement of an Overall Assessment of Erythema
	(0-3 scale) score of 0 at weeks 2, 4, and 8
	• Achievement of an Overall Assessment of Scaling
	(0-3 scale) score of 0 at weeks 2, 4, and 8
	• In subjects with a Baseline WI-NRS pruritus score
	of \geq 4, achievement of a \geq 4-point improvement from
	Baseline in WI-NRS pruritus score at weeks 2, 4,
	and 8
	• Change from Baseline in DLQI at weeks 2, 4, and 8
	• Change from Baseline in BSA affected at week 8
	• A 2-grade improvement in IGA from Baseline

Statistical Considerations:	There are approximately 184 subjects planned for this study; randomized 2:1 to ARQ-154 foam 0.3% : vehicle
	QD, stratified by study site and baseline disease severity.
	A sample size of 184 subjects will provide approximately 90% power to detect an active response of at least 55.8%, assuming 159 (86%) subjects complete the study and a vehicle response of 30%, based on two-group X^2 test of equal proportions (without continuity correction, using a 2-sided alpha of 0.10).

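### The synopsis and Section 6.1.1 claim the same 90% power for two different active response rates (55.8% and 58.5%), and neither rate gives 90% under the stated inputs

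*Protocol*

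**What the plan says.** Section 6.1.1 (Determination of Sample Size) plans for 184 subjects randomised 2:1. It states "approximately 90% power to detect an active response of at least 58.5" per cent, "assuming 159 subjects complete the study and a vehicle response of 30" per cent, using a two-group chi-square test "without continuity correction), using a 2-sided alpha of 0.10".

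The synopsis (Section 1.1, Statistical Considerations) repeats the calculation with the same sample size, completers (adding that 159 is 86% of 184), vehicle rate, test and alpha. There the claim is "approximately 90% power to detect an active response of at least 55.8" per cent.

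Two other places bear on the point. Section 6.1 sets a general two-sided significance threshold of 0.10 unless otherwise specified. Section 6.3.1 then specifies the 5% two-sided level for the primary endpoint. Section 6.1.3 adds one non-binding futility look, once the first 60 randomised subjects have had the opportunity to complete the Week 8 assessment.

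**The concern.** One set of inputs and one power figure determine one detectable response rate. The protocol gives two, 2.7 percentage points apart (58.5 − 55.8). The target difference over vehicle is therefore 25.8 points in the synopsis and 28.5 points in Section 6.1.1. The digits suggest a transposition, but nothing in the protocol says which figure was intended.

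If this were only a typing error, one of the two rates should reproduce 90%. If neither does, correcting a digit is not enough, because the stated power, the alpha or the method must also be wrong or incomplete.

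The planning effect is what justifies the trial's size. If the futility boundary spends type II error, which the protocol does not spell out, the boundary also depends on that effect.

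**Working it through.** **Inputs.** From both sample-size statements: vehicle rate p₁ = 0.30; active rate p₂ = 0.558 (synopsis) or 0.585 (Section 6.1.1); 159 completers, split 2:1 as n₁ = 53 vehicle and n₂ = 106 active; two-sided alpha 0.10 (z = 1.645). Alpha 0.05 (z = 1.960) is run as well because of Section 6.3.1.

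**Formula** (normal approximation to the uncorrected chi-square test):

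power = Φ{ [ (p₂ − p₁) − z·S₀ ] / S₁ }

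where S₀ = √[ p̄(1 − p̄)(1/n₁ + 1/n₂) ], S₁ = √[ p₁(1 − p₁)/n₁ + p₂(1 − p₂)/n₂ ], and p̄ = (n₁p₁ + n₂p₂)/159.

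**Section 6.1.1, 58.5%, alpha 0.10.**
- p̄ = (15.9 + 62.01)/159 = 0.490; S₀ = 0.0841; S₁ = 0.0791.
- (0.285 − 1.645 × 0.0841)/0.0791 = 1.855, so power = **96.8%**, against a stated figure of about 90%.

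**Synopsis, 55.8%, alpha 0.10.**
- p̄ = (15.9 + 59.148)/159 = 0.472; S₀ = 0.0840; S₁ = 0.0793.
- (0.258 − 1.645 × 0.0840)/0.0793 = 1.511, so power = **93.5%**, against a stated figure of about 90%.

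**Rate that gives 90% at alpha 0.10.** For p₂ = 0.540: p̄ = 0.460, S₀ = 0.0838, S₁ = 0.0794. (0.240 − 1.645 × 0.0838)/0.0794 = 1.286, so power = 90.1%. The detectable rate is **about 54.0%**.

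**All combinations, 159 completers at 106:53:**

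| Two-sided alpha | Power at 55.8% | Power at 58.5% | Rate giving 90% |
|---|---|---|---|
| 0.10 (sample-size statements) | 93.5% | 96.8% | 54.0% |
| 0.05 (Section 6.3.1) | 88.0% | 93.6% | 56.6% |

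**Completers needed for 90% power at 2:1:**

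| Two-sided alpha | Target 55.8% | Target 58.5% |
|---|---|---|
| 0.10 | 138 | 114 |
| 0.05 | 171 | 141 |

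None of these is 159.

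**Sensitivity.**
- Exact binomial enumeration of the uncorrected test at alpha 0.10 and 106:53 gives 93.5% and 96.8%, so the approximation is not the cause.
- Section 6.1.1 expects about 121 active and 63 vehicle subjects. Scaled to 159 completers that is about 105:54 or 104:55. Power at alpha 0.10 is then 93.6–93.8% and 96.9–97.0%.
- With all 184 subjects at 121:63, power at alpha 0.10 rises to 96.3% (55.8%) and 98.4% (58.5%).
- A continuity correction at alpha 0.10 brings 55.8% to 90.9–91.4%, but both statements exclude it. It leaves 58.5% at 95.3% or more.

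**The case against.** The strongest reply is that the check treats the design as having no interim look, whereas Section 6.1.3 adds a futility rule from the rho family with parameter 0.1. Suppose the rule spends type II error as 0.10 × t^0.1, with the look at t = 60/184. Then 0.10 × 0.894 = 0.089 of the 0.10 is spent at the interim. If the boundary is also obeyed, power at alpha 0.10 for 58.5% falls to about 89–90%, close to the stated figure, and power for 55.8% falls to about 86–88%.

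This is a possible origin for 58.5%, but it does not rescue the text. The spending function's target, the information fraction and obedience to the rule are assumptions that the protocol does not state. The rule is declared non-binding and accrual continues through it. Both sample-size statements rest the power on the two-group chi-square test alone. The synopsis figure would still be wrong, and the contradiction would remain.

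One part of the objection stands: a corrected statement should say whether the power allows for the futility look. Under the same assumptions, a 54.0% rate has about 85–86% power if the boundary is recalibrated to that rate. It has about 80% if the boundary stays where 58.5% would put it (Z of about 0.75).

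Two further points are fair. At alpha 0.10 the error is conservative, since power exceeds 90% at either rate. The expected arm sizes of 121:63 differ from an exact 2:1 split of 184 (about 123:61) by only two subjects per arm and are given as approximate, so they are not pressed here.

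**Conclusion.** The concern holds. The two statements contradict each other on the active response rate. Under the test, alpha, vehicle rate and completers that both give, neither rate has about 90% power: the figures are 93.5% (55.8%) and 96.8% (58.5%), and 90% belongs to about 54.0%.

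Of the four pairings of rate and alpha in the fixed design, only 55.8% at alpha 0.05 comes within two points of 90%, at 88.0%. That is the level Section 6.3.1 sets for the primary test. It hints that the calculation may have been intended at 5% and that 58.5% is a transposition, but it proves neither.

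On the stated inputs the trial is not underpowered at alpha 0.10, and no increase in N follows. What fails is the justification: the target difference is 25.8 or 28.5 points, and the power for the primary test lies anywhere from 88% to 97%, depending on which sentences are believed. These figures assume 159 completers at or near 2:1, an unstratified uncorrected chi-square test, and no power lost to the futility look.

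**What to change.** Decide the two-sided alpha for the primary test and make the synopsis and Sections 6.1, 6.1.1 and 6.3.1 agree. Then give one active response rate, with its recomputed power, in both sample-size statements. For 159 completers at 2:1 and vehicle 30%, ignoring the interim look, consistent wordings are:

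- alpha 0.10: 90% power to detect 54.0%, or 93.5% power to detect 55.8%;
- alpha 0.05: 90% power to detect 56.6%, or 88% power to detect 55.8%.

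If 58.5% was the intended rate, the matching powers are 96.8% (alpha 0.10) and 93.6% (alpha 0.05).

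Add one sentence saying whether the power allows for the futility look. If it does, give the assumptions about spending, timing and adherence to the rule, and the power under them.

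The cost is two corrected sentences in the sample-size text, one added sentence, and agreement of the alpha elsewhere. N stays at 184, with no change to enrolment or procedures.
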